# Feasibility of Home-Based Rehabilitation on Body Composition, some Anthropometric Measures and Muscular Strength after interruption 4-5 years of Spinal Cord Injury: Serial Cases Study on ISIS War Survivors in Iraq

## **Summary**

Background: The war in Mosul wrecked hospitals and rehab centers, leaving a gap in rehabilitation services. This resulted in a need for alternative solutions for rehabilitation. Objectives: This study aims to create a home-based rehabilitation program (HBRP) that fits the participant; surroundings, and also detect and evaluate how effective it is in improving body composition, some anthropometric measurements, and muscle strength after a (4-5) year break in rehabilitation.

Methods: This voluntary controlled trial included 18 volunteers split into three groups: 13 people with Spinal Cord Injury (SCI) their injuries time since (53.4-55) months. They joined voluntarily into Two groups, Eight in the experimental group (Exp.) and Five in the first control (1st Con.); while Five were healthy individuals in the second control (2nd Con.); all around (21.2) years old on average. The HBRP focused on muscles and whole-body joints by using the basic equipment and exercises right at the patient's homes. The program consisted of five weekly sessions with a gradually increasing achievement time of (45-120) minutes per session, participants were given rest time between exercises based on their level and severity of injury. The assessment was every three months.

Innovatively, this study stands out by introducing an HBRP tailored for individuals with SCI after interruption sustained (4 - 5) years ago. This unique approach not only addresses the challenges posed by the interruption of previous rehabilitation efforts but also seeks to uncover the efficacy of rehabilitation in these specific circumstances.

Conclusions: The study concluded that HBRP affected positively the muscles morphologically and functionally despite a stop in rehabilitation for a long period of (4-5) years for individuals with SCI.

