The physical tests were conducted using a handheld muscle tester called MicroFET2 to evaluate the strength of participants' lower extremities, head, and trunk by using unit measure kilogram (kg) 11. The Exp. group underwent a 6-month intensive rehabilitation program that involved whole-body exercises, including stretching, strength, endurance, and aerobic training, which was prepared based on previous studies 12. The program included five weekly sessions of (45-120) minutes, gradually increasing in intensity. It encompassed various exercises like bed exercises, rubber ball exercises for strength and balance, trunk flexibility exercises, crawling, rolling, ball-related movements, and exercises on parallel bars. Also, aerobic exercises targeted cardiorespiratory fitness. While weight exercises focused on the upper limbs, shoulders, chest, and back. Rest periods were personalized based on injury severity and overall health. The authors updated the exercises based on regular assessments every 3 months, tracking muscle strength and endurance. The authors created a contact link for coordination among medical, rehabilitative teams, and participants, families, overcoming some challenges within the Iraqi healthcare system.

To address complex complications like bed sores, renal infections, and muscle atrophy, the authors followed the method of psychological support. This method aimed to stimulate patients, willpower, encouraging them to overcome complications and emphasizing the benefits of rehabilitation for improved overall health and independence, by made WhatsApp group was created to facilitate information sharing and provide visual evidence of successful cases, inspiring and encouraging participants. Furthermore, the participant weight and BMI were monitored due to the potential impact of factors such as limited movement and hormonal changes on weight fluctuations, as recommended in previous studies.

The study highlights the participants the participants fidelity to treatment, as evidenced by positive outcomes and sustained progress beyond the conclusion of the therapeutic experiment. The participants demonstrated loyalty through ongoing communication with the main author, seeking feedback on their rehabilitation stages who reach it. Notably, some participants achieved the significant milestone of walking by standard walker with the assistive device Knee-Ankle-Foot-Orthosis (KAFO).

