## **Statistic Analyze**

The study used Two-way ANOVA repeated measures as a statistical analysis method, with effect size and improvement percentage (IP) as measures, and (IBM-SPSS statistics processor version 20) for data analysis. A statistical significance level of  $P \le 0.05$  (alpha) was used.

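### The protocol was written after the results, so it does not show that its ANOVA at P ≤ 0.05 was pre-specified, and its sustained-progress and walking statements have no described measurement behind them

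*Protocol*

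**What the plan says.** The Conclusions paragraph of the Protocol's Summary states a finding: "The study concluded that HBRP affected positively the muscles morphologically and functionally". The Background refers to the text as an article, and Methods and Statistic Analyze describe completed work. Statistic Analyze names a two-way repeated-measures ANOVA with effect size and improvement percentage. It adds "A statistical significance level of" P ≤ 0.05.

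On timing, the Summary says "The assessment was every three months" and Methods says "The Exp. group underwent a 6-month intensive rehabilitation program". The list of main contributions also gives six months as the length of the programme. No later visit is described.

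Methods nevertheless describes fidelity to treatment "as evidenced by positive outcomes and sustained progress beyond the conclusion of the therapeutic experiment". The next sentence says "The participants demonstrated loyalty through ongoing communication with the main author", and the paragraph ends by noting that "some participants achieved the significant milestone of walking by standard walker" with an orthosis.

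The outcomes named under the two study questions are body composition (weight, BMI), anthropometric measures and muscle strength.

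The combined protocol and SAP is a future-tense form for a community survey, with case-control ticked as its design. Section 5.9 lists a pre-post t-test, Pearson and Spearman correlation, LSD and descriptive statistics, with further tools to be settled later.

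**The concern.** A P value has its nominal error rate only if the outcome and the test were fixed without sight of the data. A plan that contains its own conclusion cannot serve as evidence of that. Methods describes several circumferences, strength tests of the limbs, head and trunk, and repeated visits, and no primary outcome is named. There was therefore room to choose, and the documents do not show when the choice was made.

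The sustained-progress and walking statements raise a second problem. A reader could take them as evidence of lasting and functional benefit, yet no measurement that could support either is described. At stake is whether the trial may present its P values as confirmatory and whether it may say anything about benefit after month 6.

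**Working it through.** The plan gives no sample-size, power or error-rate figure on this point, so there is nothing to reproduce. The check sets the texts side by side, with two small calculations.

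**1. When was the text written?** The Summary contains a conclusion, the Background calls the text an article, and Methods reports positive outcomes. The Protocol was therefore written with results in hand. That dates the text. It does not date the choice of test.

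**2. Does any forward-looking text name the test?**

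| Item | Protocol, Statistic Analyze | Combined protocol and SAP, section 5.9 |
|---|---|---|
| Tense | past | future |
| Study described | home-based rehabilitation, three groups | community survey, case-control |
| Main test | two-way repeated-measures ANOVA | pre-post t-test |
| Other tools | effect size, improvement percentage | correlations, LSD, descriptives, others left open |
| Alpha | 0.05 | none stated |

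The tests differ in kind. A pre-post t-test examines change within one group. A two-way repeated-measures ANOVA can also test whether change differs between groups. LSD often follows an ANOVA, but listing it does not specify this model. The form therefore does not show pre-specification.

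**3. What assessment schedule is described?** The interval is 3 months and the programme lasts 6 months. Taking month 0 as baseline (an assumption), the visits are at months 0, 0 + 3 = 3 and 3 + 3 = 6. Described assessments after month 6: none. This is inferred from the interval and the programme length; the text does not say in words that follow-up stopped there.

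**4. What supports the walking statement?** Walking is not among the outcomes under the study questions. No number, date or control figure is given. The possible denominators are 8 experimental and 5 SCI control participants (8 + 5 = 13 with SCI; with 5 healthy controls, 18 in all).

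**5. Why prior choice matters, for scale only.** The number of tests k is not in the documents, so it is an assumption here. For k independent tests at 0.05, the chance of at least one false positive is 1 − 0.95^k:

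| k | 1 | 3 | 5 | 10 | 20 |
|---|---|---|---|---|---|
| Chance | 0.05 | 0.143 | 0.226 | 0.401 | 0.642 |

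Outcomes measured in the same people are likely to be positively correlated, which would put the true figure between 0.05 and the value shown.

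**The case against.** The best defence is that past tense shows when a document was written, not when its test was chosen. A reader might infer that the ANOVA was picked after seeing the data. The documents do not establish that, and a dated earlier plan may exist. The combined form also contains some forward-looking content on the same ground: section 4.3 mentions physical and functional tests, mostly at home, and section 5.4 lists mass and BMI. This stands. What can be said is that pre-specification is not shown, not that it is disproved. The form does not settle the matter the other way either, because it describes a differently titled survey and does not name this ANOVA.

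Second, the sustained-progress statement is offered as evidence of fidelity to treatment, not as an outcome. Neither durability nor walking appears in the Summary's conclusion or in the study questions. This also stands, so a reader should not infer that these statements biased the stated conclusion. They remain claims of benefit in a trial document with no described measurement behind them.

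Third, a reader might infer that there are no data at all after month 6, or that those who kept in touch were a self-selected subset of the 8. The documents support neither. Informal communication is mentioned, and Methods attributes it to the participants without giving a number, subset or group. The supportable statement is that no scheduled or defined assessment after the programme is described. The collection window in section 4.1 of the form (1 December 2019 to 31 January 2022) is longer than six months, but it belongs to the survey and defines no follow-up visit.

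Finally, neither document calls the analysis confirmatory, and the Protocol's title speaks of feasibility and serial cases. That is fair, and it makes an exploratory label easy to accept. The Summary's conclusion is nonetheless worded as an established effect.

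**Conclusion.** The concern holds in limited form. The Protocol was written after the results were known. Neither document shows that the two-way repeated-measures ANOVA at P ≤ 0.05 was specified beforehand, and the one future-tense analysis section names other methods and no alpha. The sustained-progress statement has no described assessment after month 6 behind it, and the walking statement has no count, date or control figure.

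No numerical size can be given for the loss of error control, because the number of tests is not stated; the error rates in the working are illustrative and assume independence. The month-6 limit assumes that the three-monthly schedule ended with the programme. The point should be addressed because it changes what the trial may claim. A dated earlier plan naming this ANOVA would remove the part about pre-specification, but not the part about durability and walking.

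**What to change.** - Date the Protocol and label it retrospective. Simply deleting the conclusion would hide the fact that results were known.
- Cite a dated earlier plan that names this ANOVA. If there is none, label the analysis exploratory. The sponsor need not declare that the test was chosen after data collection unless that is so.
- Report every body-composition, circumference and strength outcome measured, with estimates and 95% CIs, at each time point at which each group was actually assessed. The healthy controls are described only as completing their tests at college, so 3- and 6-month results should not be presumed for them.
- Limit the conclusion to change up to month 6.
- Remove the sustained-progress statement, or mark it as informal and unmeasured.
- Report walking only as a count out of 8 experimental and out of 5 SCI control participants, or remove it.

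The cost is rewording and fuller tabulation of measurements already taken. The downside is that the trial cannot present its P values as confirmatory, unless an earlier plan is produced, and cannot claim lasting benefit.

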## The study raises two questions

Does the home-based rehabilitation program (HBRP) affect people with spinal cord injury through interruption of rehabilitation for 4-5 years?

Is the HBRP effects on variables such as body composition (Weight, BMI); Anthropometric Measures, and Muscle strength?

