#### Methods

This voluntary controlled trial included 18 volunteers split into three groups: 13 people with Spinal Cord Injury (SCI) their injuries time since (53.4-55) months. They joined voluntarily into Two groups, eight in the experimental group (Exp.) and Five in the first control (1st Con.); while five were healthy individuals in the second control (2nd Con.); all around (21.2) years old on average. As a first procedure, detailed interviews were conducted with each participant at the beginning of the study to gather information about their physical, psychological, and social well-being. This information helped the authors create personalized rehabilitation plans for each participant to ensure their

participation in the study for the entire 6 months period. Through our study objectives, the authors used body composition such as height, weight, BMI and some anthropometric measurements for body parts circumferences by using tape measurements, similar to a previous study by Akita et al. Also, muscle strength tests were performed on participants' lower and upper extremities, head, and trunk to measure various movements. The 2nd control group completed their measurements and tests at college. Additionally, a clinical test using the American Spinal Injury Association scale (ASIA) was conducted on each participant to assess sensory feeling and voluntary movement potential on both sides of the body.

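### The conclusion that muscle changed morphologically rests on weight, BMI and tape girths, which cannot distinguish muscle from fat or fluid and have no stated direction of improvement

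*Protocol*

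**What the plan says.** The Protocol's Summary sets the aim as to "detect and evaluate how effective it is in improving body composition, some anthropometric measurements, and muscle strength". Its closing sentence concludes that "HBRP affected positively the muscles morphologically and functionally despite a stop in rehabilitation for a long period of (4-5) years".

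The second study question shows what body composition means here: "Is the HBRP effects on variables such as body composition (Weight, BMI); Anthropometric Measures, and Muscle strength". The Methods section adds height and tape girths: "the authors used body composition such as height, weight, BMI and some anthropometric measurements for body parts circumferences by using tape measurements". It also explains why two of these were followed: "the participant weight and BMI were monitored due to the potential impact of factors such as limited movement and hormonal changes on weight fluctuations". Strength is measured separately, with a "handheld muscle tester called MicroFET2 to evaluate the strength of participants' lower extremities, head, and trunk", in kilograms.

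The section headed Statistic Analyze specifies a two-way repeated-measures ANOVA "with effect size and improvement percentage (IP) as measures". It gives no formula for improvement percentage and no beneficial direction for any variable.

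The Combined protocol and SAP, section 5.4, uses the word morphological for mass, length and BMI. Its analysis section (5.9) does not mention improvement percentage, and it draws no conclusion about muscle.

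**The concern.** There are two problems.

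**Measure and claim do not match.** The conclusion is about the form of the muscles. Weight and BMI describe the whole body. A tape girth encloses muscle, bone, fat and fluid together. The supplied text describes no method that separates lean tissue from fat. A fat gain in an inactive limb and a muscle gain in an exercised one can give the same reading.

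**Improvement has no stated sign.** More strength is better. For weight, BMI and girth the Protocol does not say whether a rise or a fall is better, and its own text points both ways. It lists muscle atrophy among the complications to be addressed, which would make a rise welcome. It also ties weight change to limited movement and hormonal factors, which could make a rise unwelcome. If improvement percentage is applied to these outcomes, the label has to be chosen after the result is known.

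At stake is the morphological half of the headline conclusion.

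**Working it through.** The documents give no improvement percentage, standard deviation, expected effect or sample-size figure for these outcomes, so there is no stated result to reproduce. The check is a comparison of texts and two illustrations. **All body dimensions below are assumptions; the documents give none.**

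**1. Claim against measure**

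| Part of the conclusion | Measure in the Protocol | Can it establish the claim? |
|---|---|---|
| Function of muscle | Strength tests, kg | It measures function directly |
| Morphology of muscle | Tape girths | Indirectly at most; tissues not separated |
| Morphology of muscle | Weight, BMI | No; whole-body size only |

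**2. Weight and BMI.** Take percentage change = 100 × (after − before) / before. BMI = weight / height². With height fixed, height² cancels, so the percentage change in BMI equals that in weight. From 60 to 63 kg, both give 3/60 = +5.0% at heights of 1.6, 1.7 and 1.8 m; from 60 to 57 kg, both give −5.0%. The two outcomes therefore carry one piece of information about percentage change.

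For an assumed 60 kg participant:
- 2 kg of fat gained: 2/60 = +3.3%
- 2 kg of muscle gained: 2/60 = +3.3%
- 2 kg of muscle gained and 2 kg of fat lost: 0/60 = 0%

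**3. Girth.** Treat a limb as a circle of girth G with an even fat layer of thickness t. The radius is R = G / (2 × pi). The inner (muscle plus bone) area is pi × (R − t)². Its relative change is [(R₁ − t₁) / (R₀ − t₀)]² − 1. Assumed ranges: G from 35 to 55 cm, t from 0.5 to 1.5 cm.

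Example with G = 45 cm, t = 1.0 cm and a girth gain of 2 cm:
- R₀ = 45 / (2 × pi) = 7.162 cm and R₁ = 47 / (2 × pi) = 7.480 cm
- Fat thickness unchanged: (6.480 / 6.162)² − 1 = +10.6%
- Fat thickness up 0.5 cm: (5.980 / 6.162)² − 1 = −5.8%

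Over the assumed ranges:

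| Girth reading | Change in fat thickness | Change in inner area |
|---|---|---|
| +2 cm (2/55 = +3.6% to 2/35 = +5.7%) | none | +7.9% to +16.3% |
| +2 cm | +0.32 cm, that is 2 / (2 × pi) | none |
| +2 cm | +0.5 cm | −4.4% to −8.7% |
| unchanged (0%) | −0.3 cm | +7.4% to +15.3% |

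A girth change alone therefore fixes neither the size nor the sign of a change in muscle.

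**The case against.** The best defence is that readers are told what was measured. The second study question spells out body composition as weight and BMI, and the Combined protocol and SAP uses morphological for body size, so the authors may mean no more than that. This explains the wording but does not rescue it: the concluding sentence applies the word to the muscles, not to the body.

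Second, girth and strength rising together in the experimental group, relative to the SCI controls, would point towards muscle growth. That is fair. A reader might infer that the morphological claim has no support whatever the data show, and that goes too far. The support would be indirect and would still not separate the tissues.

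Third, a reader might infer that the Protocol reports improved body composition, or that it expressly applies improvement percentage to weight and girth. The documents do not support either. Improved body composition is an aim and a question, not a stated result. Improvement percentage is named once, for the study as a whole, and is not tied to any outcome.

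Fourth, the control groups and the reference to atrophy give some idea of what a good result might look like. They are reference points, but they do not define a direction for each variable.

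Finally, the illustrations use assumed figures and show no effect on any result of this trial. That is correct. They show only what such measures can and cannot establish.

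**Conclusion.** The concern holds in a limited form. The Protocol concludes that the muscles changed for the better morphologically, and none of the size measures in the supplied text can distinguish muscle from fat or fluid. Weight, BMI and girth also have no stated beneficial direction, so labelling a change in them as improvement would be post hoc.

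The functional half of the conclusion is not challenged here. Nor do the documents show that fat gain was in fact reported as muscle growth. The ring model shows that, on plausible but assumed dimensions, one girth reading is compatible with inner-area changes of opposite sign; the exact percentages depend on those assumptions, and the qualitative point does not. That no tissue-separating method is described is judged on the supplied text only.

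**What to change.** All changes are in the Protocol; on this point the Combined protocol and SAP needs none.

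- **Summary, conclusion:** limit it to muscle strength (function) and to changes in weight, BMI and circumference. Drop the statement about muscle morphology.
- **Title, objective, second study question and Methods:** call weight and BMI anthropometric measures rather than body composition.
- **Statistic Analyze:** report weight, BMI and circumferences as signed changes in kg, kg/m² and cm, experimental group against SCI control group, with 95% confidence intervals and no improvement label. Give the formula for improvement percentage and use it only for strength, where higher is better.

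This needs no new measurement, and in particular no imaging. The cost is a narrower conclusion. With 8 and 5 participants in self-selected groups, the intervals are likely to be wide, and they do not remove the effects of self-selection.

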## **Background**

Spinal Cord Injury (SCI) is a complex pathology that requires skills in assessment, treatment, and rehabilitation, SCI is a large topic area. Approximately (90%) of SCI cases occur as a result of traumatic causes Globally, incidence varies from 40 to 80 cases per million population. So, people with injuries consequences are becoming more frequent due to conflicts and wars. In Iraq, the main reasons for the occurrence of this injury due to were the Islamic State in Iraq and Syria (ISIS) war, which is resulting in enormous unmet rehabilitation needs. Alarcon Cieza found in his study Rehabilitation the health strategy of the 21st Century that the rehabilitation stakeholders need to bring

together the distinct portraits of rehabilitation under the concept of functioning because much of these unmet needs are concentrated amongst the poorest populations in low-and middle-income countries and conflict-affected settings, which are often ill-equipped to cope with these increasing needs for rehabilitation services. Iraq is regarded as one of these countries its health sectors, including rehabilitation, have been exhausted due to wars and armed violence. However, rehabilitation can be effective across almost all conditions, therefore in some ways, we should have been so backwards about recognizing the effectiveness of rehabilitation for many years.

It is worth noting that healthcare problems are among the most complex problems faced by human beings, especially under conditions of war, armed conflicts, terrorist operations and post-war secretions. In low-middle income countries, so many people would die from SCI within a year, two years, or three years from infection, renal failure, and so on, and also people could not work, and they either were at home or in residential care, just waiting to die. One of the defining characteristics of rehabilitation is that there are many interventions; in contrast to most medical conditions, rehabilitation can take place in any setting as a process for problem-solving.

